To be eligible for the study, a patient must be, in the opinion of the investigator, a candidate for at least 1 year of continuous androgen deprivation therapy for the management of androgen-sensitive advanced prostate cancer and must not be a candidate for surgical therapy. Eligible patients include those with evidence of biochemical relapse (rising PSA) following local primary intervention with curative intent, newly diagnosed metastatic disease (excluding metastases to the brain), and/or advanced localized disease. Patients may receive radiotherapy, cryotherapy or high frequency ultrasound no sooner than 2 months after initiation of androgen deprivation therapy. Patients may be included if they have not previously received androgen deprivation therapy for more than 18 months, and if the androgen deprivation therapy was completed at least 3 months prior to the baseline visit. If the dosing interval of the depot is longer than 3 months, then the prior androgen deprivation therapy must have been completed at least as long as the dosing interval of the depot. Patients previously treated with taxanes or expected to receive taxanes after initiation of androgen deprivation therapy are excluded, as are patients receiving androgen deprivation therapy adjuvant or neoadjuvant to radiotherapy as primary definitive therapy. Baseline serum testosterone must be ≥ 150 ng/dL (1.50 ng/mL or 5.2 nmol/L) to be enrolled.

Patients enrolled in this study will be randomized 2:1 to receive oral relugolix 120 mg once daily following a loading dose of 360 mg on Day 1 or 3-M depot of leuprolide acetate 22.5 mg (or 11.25 mg in Japan, Taiwan, and China). After randomization, patients on the leuprolide acetate arm may receive an antiandrogen for the first 4 weeks or longer if indicated in the opinion of the investigator. Randomization will be stratified by geographic region, presence of metastatic disease, and age.

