1. Overall survival: Overall survival defined as time from randomization to date of death prior to data cutoff date. Kaplan-Meier methods will be used to describe survival distributions;
2. The effect of polymorphisms in germline genes related to the hypothalamic-pituitary-androgen pathway, prostate cancer risk, or drug metabolizing enzymes and transporter proteins on the efficacy and safety of relugolix will be described in a separate statistical analysis plan.

The methods and procedures needed to maintain a study-wide 2-sided type I error rate of 0.05 across primary and secondary endpoint testing will be described in the statistical analysis plan.

Pharmacokinetics

Relugolix plasma concentrations will be summarized and described using population PK methods. Plasma PK parameters in a subset of patients from China (if enrolled) and Japan will be determined using noncompartmental methods.

Safety

Safety assessments, including adverse events, vital signs, clinical laboratory tests, and ECGs, will be summarized for the treatment-emergent period. The treatment-emergent period is defined as the time from first dose of study drug through 30 days after the last dose of relugolix or 12 weeks plus 30 days after the last dose of leuprolide acetate. Safety analyses will be based on all randomized patients who receive any amount of study drug (Safety population). Drug exposure will be summarized by descriptive statistics. Severity of all treatment-emergent adverse events will be evaluated by the investigator based on the National Cancer Institute's Common Terminology Criteria for Adverse Events (CTCAE) and will be coded to preferred term, higher-level term, and system organ class using the Medical Dictionary for Regulatory Activities (MedDRA). The number and percentage of patients with adverse events will be presented by MedDRA system organ class and preferred term, relationship to study drug, and severity. Descriptive rather than inferential statistics will be used. Laboratory values also will be classified by toxicity grade based on the National Cancer Institute's CTCAE. Laboratory shift tables of baseline versus post baseline results will be produced.

An independent Data and Safety Monitoring Board will monitor all available safety data on a periodic basis. The roles and responsibilities of the Data and Safety Monitoring Board will be described in detail in a separate charter.

Sample Size

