Hematology	X	X						X		X		X		X	X ^f	X				
Chemistry	X	X				X		X		X		X		X	X ^f	X				

Period	Screening Visit	Treatment Period Visits															Follow-up ^{a,c}		
		Safety ^b		Testosterone Recovery															
Visit Name	Screening	Baseline Day 1	Day 4	Wk 2 ^q	Wk 3	Wk 5	Wk 9	Wk 13	Wk 17 and 21	Wk 25	Wk 29 and 33	Wk 37	Wk 41 and 45	Wk 49 ^e	Un-scheduled	30-Day	60-Day	90-Day	
Study Day	-28 to -1	1	4	8	15	29	57	85	113 and 141	169	197 and 225	253	281 and 309	337		EOT + 30 days	EOT + 60 days	EOT + 90 days	
Visit Window	Not applicable	± 2 days		± 7 days															
Lipid & HbA1c ^k	X									X					X	X ^r	X		
PSA	X	X	X	X	X	X	X	X	X	X	X	X	X	X	X ^r	X	X	X	
Serum Testosterone	X	X	X	X	X	X ^l	X ^r	X	X	X									
LH/FSH		X	X			X				X					X	X ^r	X	X	X
SHBG/DHT		X				X				X					X	X ^r			X
Blood Sample for Relugolix PK ^{m,n}		X ^{m,n}	X ⁿ	X ⁿ		X ^m	X ^r												
Blood Sample for DNA ^o		X														X ^r			
Health Status Survey ^p															X	X ^r			

Abbreviations: 3-M, 3-month; BMI, body mass index; CT, computed tomography; DHT, dihydrotestosterone; DNA, deoxyribonucleic acid; ECG, electrocardiogram; ECOG, Eastern Cooperative Oncology Group; EORTC, European Organization for Research and Treatment of Cancer; EOT, end of treatment; EuroQol EQ-5D-5L, European Quality of Life 5-Dimension 5-Level; FSH, follicle-stimulating hormone; HbA1c, hemoglobin A1c; LH, luteinizing hormone; MRI, magnetic resonance imaging; PK, pharmacokinetics; PSA, prostate-specific antigen; SHBG, sex hormone binding globulin

- The study day in which the Follow-up visit occurs is not specified in the table because these visits occur relative to when the patient takes his last dose of study drug. The End of Treatment (EOT) is defined as the last dose of relugolix or 12 weeks after the last leuprolide acetate injection.
- May occur earlier for patients who are starting alternative androgen deprivation therapy, or do not complete 12 weeks of study treatment. Adverse events, serious adverse events, and concomitant medications should continue to be collected and recorded through 30 days after the End of Treatment. All other study procedures should be completed before the start of alternative androgen deprivation therapy.

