- j. Collect serious adverse event information from the time of signed informed consent through the Safety Follow-up Visit, which is through 30 days after the last dose of relugolix or 12 weeks and 30 days after the last injection of leuprolide acetate, or the date of initiation of another investigational agent or hormonal therapy or surgical intervention, whichever occurs first. Collect nonserious adverse event information from the Baseline Day 1 visit (or from the time of signed informed consent if event was related to a screening study procedure through approximately 30 days after the last dose of relugolix or 12 weeks and 30 days after the last injection of leuprolide acetate, or the date of initiation of another investigational agent or hormonal therapy or surgical intervention, whichever occurs first).
- k. Blood samples must be obtained fasting; nothing to eat or drink (other than water) for at least 9 hours prior to obtaining the sample.
- l. All testosterone samples obtained from Week 5 and beyond are to be collected during a \pm 7-day window.
- m. Blood samples for PK analysis will be collected for all patients assigned to the relugolix treatment arm. Samples will be collected predose, approximately 24 hours after the previous dose. Patients may be dosed in the clinic at these visits, provided the dose can be administered at least 2 hours after food; food should be withheld for 1 hour after dosing.
- n. A subset of patients from China (if enrolled) and Japan will have additional samples collected predose, and 0.5, 1, 2, 4, 6, 8, 12, and 24 hours post-dose on Day 1 and Week 2 visits. Patients will be dosed in the clinic at these visits. The dose will be administered at least 2 hours after food; food should be withheld for 1 hour after dosing. A predose sample (approximately 24 hours after the previous dose) also will be collected at the Day 4 visit. Patients may be dosed in the clinic at the Day 4 visit, provided the dose can be administered at least 2 hours after food; food should be withheld for 1 hour after dosing.
- o. The blood sample for DNA should be collected at the Baseline Day 1 visit, but may be collected at any visit if it is missed at that visit.
- p. During the final weeks prior to database lock, sites will be asked to contact all study participants or their immediate family regarding the current health status of previously enrolled/completed study patients.

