6.4. Follow-up Period

The study day in which the Follow-up visit occurs is relative to when the patient takes his last dose of study drug. The End of Treatment is defined as the last dose of relugolix or 12 weeks after the last leuprolide acetate injection.

30-Day Safety Follow-up Visit (Visit Window ± 7 Days)

A Safety Follow-up visit should occur 30 days after the End of Treatment and may occur earlier for patients who are starting alternative androgen deprivation therapy or do not complete 12 weeks of study treatment. Adverse events should continue to be collected and recorded through 30 days after the last dose of study drug or the date of initiation of another investigational agent or hormonal therapy or surgical intervention, whichever occurs first. Serious adverse events and concomitant medications will be collected from the signing of the informed consent form until the Safety Follow-up visit approximately 30 days after the last dose of study drug.

All other study procedures should be completed before the start of alternative androgen deprivation therapy.

The following assessments will be performed:

- Patient-reported questionnaires
 - Patients will complete the questionnaires on the tablet provided before other study procedures, such as blood draws and physical examinations, are performed;
- Vital signs and weight;
- 12-lead ECG;
- ECOG performance assessment;
- Symptom-based physical examination;
- Laboratory collection (see Section 1.1); and
- Concomitant medications and adverse events.

Testosterone Recovery Visit (Visit Window ± 7 Days)

Patients who have started alternative androgen deprivation therapy will not participate in the 60- and 90-day follow-up visits. Approximately 100 patients randomized to receive relugolix and approximately 50 patients randomized to receive leuprolide acetate who complete the 48 weeks of study drug treatment and, in the opinion of the investigator, are candidates for intermittent androgen deprivation therapy will be included in the Testosterone Recovery 60- and 90-day Follow-up visits. These patients will discontinue relugolix after 48 weeks of treatment and will be offered a period off androgen deprivation therapy.

The following assessments will be performed:

- Patient-reported outcome questionnaires
 - Patients will complete the questionnaires on the tablet provided before other study procedures, such as blood draws and physical examinations, are performed;
- Vital signs;

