7.2.1. Adverse Event Reporting Period

Adverse events will be collected from the time the first dose of study drug is administered until the Safety Follow-up visit approximately 30 days after the last dose of relugolix or 12 weeks plus 30 days after the last leuprolide acetate injection, or the date of initiation of another investigational agent or hormonal therapy or surgical intervention, whichever occurs first.

Serious adverse events will be collected from the signing of the informed consent form until the Safety Follow-up visit approximately 30 days after the last dose of relugolix or 12 weeks plus 30 days after the last leuprolide acetate injection, or the date of initiation of another investigational agent or hormonal therapy or surgical intervention, whichever occurs first. Serious adverse events reported to the investigator after the safety reporting period should be reported to the sponsor if the investigator assesses the event as related to the study drug treatment.

Any event occurring between signing of the informed consent form and the first dose of study drug will be recorded as medical history and in the patient’s clinical record for any patient who

continues to meet eligibility criteria and proceeds to dosing with study drug; the exception to this includes procedure-related pretreatment-emergent events which should be recorded as adverse events in the electronic data capture (EDC) system for those patients who remain eligible for study participation.

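### The protocol gives incompatible rules for when adverse-event collection ends, and two of them stop serious-event collection inside the window the safety analysis counts

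*Protocol*

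**What the plan says.** All passages compared here come from the amended version of the protocol, so nothing below is a difference between versions.

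- **Section 6.4 (30-Day Safety Follow-up Visit), adverse events:** "Adverse events should continue to be collected and recorded through 30 days after the last dose of study drug". Collection ends sooner if new therapy or surgery comes first.
- **Section 6.4, serious adverse events:** collected "until the Safety Follow-up visit approximately 30 days after the last dose of study drug", with no early stop.
- **Section 7.2.1:** on relugolix, collection runs for 30 days past the final dose. For leuprolide the text reads "12 weeks plus 30 days after the last leuprolide acetate injection, or the date of initiation of another investigational agent or hormonal therapy"; surgery is a further trigger. The early stop applies to adverse and serious adverse events alike: "or the date of initiation of another investigational agent or hormonal therapy or surgical intervention, whichever occurs first".
- **Section 1.1, footnote j:** the same rule as 7.2.1 for both kinds of event, surgery included. For leuprolide it reads "12 weeks and 30 days after the last injection of leuprolide acetate, or the date of initiation of another investigational agent or hormonal therapy".
- **Section 1.1, footnote b,** which concerns men moving to alternative androgen deprivation or treated for under 12 weeks: "Adverse events, serious adverse events, and concomitant medications should continue to be collected and recorded through 30 days after the End of Treatment".
- **Synopsis, Safety:** "The treatment-emergent period is defined as the time from first dose of study drug through 30 days after the last dose of relugolix". On leuprolide, a further 12 weeks are added to those 30 days. No early stop is stated.

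End of Treatment is the last relugolix dose, or 12 weeks after the last leuprolide injection (Section 6.4).

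**The concern.** Sites have to know when to stop recording events, and here the answer depends on which page they open. The sharpest conflict concerns serious events in a man who starts other androgen deprivation soon after study treatment: 7.2.1 and footnote j say stop, while 6.4 and footnote b say continue. Eligibility requires candidates for at least one year of continuous androgen deprivation, and study treatment lasts 48 weeks, so moving to another therapy is an ordinary course of events.

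The analysis adds to the problem. The treatment-emergent window runs its full length for every patient, so it counts days on which 7.2.1 tells sites not to collect. An absence of recorded events on those days would be read as an absence of events. A statistical analysis plan could shorten the analysis window to match, but it cannot restore events that were never recorded.

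**Working it through.** **Rules side by side**

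| Source | Adverse events end | Serious adverse events end | Early stop at new therapy or surgery |
|---|---|---|---|
| 6.4 | last dose + 30 days | about last dose + 30 days | AEs yes, SAEs no |
| 7.2.1 | relugolix + 30 days; leuprolide + 12 weeks + 30 days | same | both |
| Footnote j | as 7.2.1 | same | both |
| Footnote b | End of Treatment + 30 days | same | neither |
| Treatment-emergent window | relugolix + 30 days; leuprolide + 12 weeks + 30 days | same | neither |

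**Calendar.** Week *w* Day 1 is Study Day 7(*w* − 1) + 1.
- Last leuprolide injection, Week 37 Day 1 (Synopsis): 7 × 36 + 1 = Day 253.
- Leuprolide End of Treatment: 253 + 84 = Day 337, which is Week 49 Day 1. This reproduces the protocol's own schedule.
- Last relugolix dose, Week 48 Day 7 (Figure 4-1): Day 336.
- Full window for completers: 336 + 30 = Day 366 on relugolix; 337 + 30 = Day 367 on leuprolide.

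**Effect of the early stop.** If new therapy starts *t* days after the last dose, the days lost from the treatment-emergent window are max(0, 30 − *t*) on relugolix and max(0, 114 − *t*) on leuprolide, where 114 = 84 + 30.

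- Completers who switch on Day 337: relugolix *t* = 1, so 29 days are lost; leuprolide *t* = 84, so 30 days are lost. The arms are about equal.
- Early discontinuers who start new therapy at *t* = 14: 30 − 14 = 16 days on relugolix and 114 − 14 = 100 days on leuprolide.
- At *t* = 30: 0 and 84 days.

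The values of *t* for early discontinuers are illustrations. The documents do not say when, or how often, such men start new therapy.

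**One patient.** A relugolix completer starts other androgen deprivation on Day 346 and has a non-fatal serious event, judged unrelated, on Day 356. Section 6.4 and footnote b require it to be collected. Section 7.2.1 and footnote j do not. It lies inside the treatment-emergent window, which runs to Day 366.

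**The 6.4 anchor.** Section 6.4 omits the 12-week leuprolide extension. Read literally, it ends leuprolide collection on 253 + 30 = Day 283 instead of Day 367, a difference of 84 days. That would exclude the Week 45 visit (Day 309), the Week 49 visit (Day 337) and the 30-day visit. Yet the Schedule of Activities and Sections 6.3 and 6.4 list adverse events at all three. Section 6.4 also defines End of Treatment with the 12 weeks included, and places the safety visit 30 days after it. The literal reading therefore contradicts its own section.

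**The case against.** Several points on the other side stand.

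- Stopping at a new therapy has a rationale: later events are hard to attribute to study drug. The error is the inconsistency, not the idea of a stop.
- Section 6.4 lets the safety visit take place before alternative androgen deprivation starts, so these men still have a closing assessment.
- Section 7.2.1 keeps late serious events reportable if the investigator judges them related.
- The Health Status Survey contacts all participants or their families, with records and registries as back-up, so deaths should be found.
- Safety summaries are descriptive, so no formal test is affected.

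Four stronger readings may tempt a reader, and the documents do not support them:

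1. That leuprolide loses 84 of 366 days (23%) in one arm only. This needs the literal 6.4 anchor, which the visit schedule, 7.2.1, both footnotes and the End of Treatment definition all contradict. It is a wording slip to correct, not an expected loss.
2. That collection ends when a permitted on-study drug starts, for example because "patients on the leuprolide acetate arm may receive an antiandrogen for the first 4 weeks or longer". The clause is not limited to the period after treatment, so it needs clarifying. But this antiandrogen is part of the comparator regimen, and enzalutamide users are told to remain on study, with adverse events scheduled at every later visit.
3. That 84% of patients are affected. The figure 915 − 150 = 765 counts everyone outside the planned testosterone-recovery subset. It is a ceiling that includes men who start nothing within 30 days.
4. That the early stop biases the comparison in general. Among completers who switch at Week 49 the loss is about equal.

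None of this tells a site which rule to follow for serious events after a switch.

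**Conclusion.** The protocol is wrong as written. It has incompatible end-of-collection rules, including a direct conflict over serious events, and an analysis window that covers days on which two of the rules forbid collection.

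The exposure is up to about 30 days per completer who starts other therapy straight after study treatment, similar in both arms. It can be longer on leuprolide for early discontinuers, because their window is 114 days after the last injection against 30 days after the last relugolix dose. The total cannot be stated: it depends on which passage sites follow and on the share and timing of new therapy, and the documents give neither. The data at risk are mainly non-serious adverse events and non-fatal serious events judged unrelated. The documents do not support a claim of missed deaths or of a large one-arm loss.

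The point still matters because events not collected cannot be recovered at analysis, and the remedy is cheap.

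**What to change.** Put one rule in Sections 6.4 and 7.2.1 and footnotes b and j: collect adverse and serious adverse events through 30 days after End of Treatment as already defined, whether or not new therapy or surgery has begun. This is the footnote b rule and matches the treatment-emergent window. In 6.4, replace the last-dose anchor with End of Treatment, so that the 12 weeks for leuprolide are included.

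Record the start date of any new therapy or surgery, so that later events can be flagged or analysed separately. Section 6.6.2.6 already records medications and procedures over the same period, so little new data capture is needed.

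If the sponsor prefers to keep an early stop for non-serious events, apply the same stop to the treatment-emergent definition, and state that it is not triggered by antiandrogen, enzalutamide or surgery that the protocol permits during study treatment.

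The cost is an amendment of wording, a site instruction, and some additional event reports after new therapy starts, a number of which will reflect that therapy.

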6.5. Unscheduled Visits

Unscheduled visits may be performed at any time during the study whenever necessary to assess for or follow-up on adverse events, at the patient's request, or as deemed necessary by the investigator. The following activities should be completed at an Unscheduled visit: recording of the date and reason for the visit in the patient's source documents, concomitant medication review and evaluation of adverse events. In addition, procedures such as vital signs, weight, symptom-directed brief physical examination, central safety laboratory assessment and collection of a PK sample if indicated, 12-lead ECG, study drug compliance and dispensation, etc. may be conducted as needed. See Schedule of Events (see Section 1.1) for tests that may be performed if indicated at an unscheduled visit. Consult with the medical monitor, if needed, to discuss Unscheduled visit testing.

6.6. Study Procedures

6.6.1. Efficacy-Related Procedures

6.6.1.1. Pharmacodynamics Sample Collection

Blood samples for the pharmacodynamic analysis of serum LH, FSH, testosterone, dihydrotestosterone, sex hormone binding globulin, and PSA will be collected predose at the visits indicated in the Schedule of Activities in the protocol synopsis (see Section 1.1). These pharmacodynamic samples will be analyzed at a central laboratory. Testosterone samples may be analyzed at a second laboratory to confirm non-castrate levels (Section 1.1).

Serum LH, FSH, dihydrotestosterone, sex hormone binding globulin, and PSA samples will be analyzed at a central laboratory.

PSA will also be used to evaluate biochemical progression per Prostate Cancer Clinical Trials Working Group 3 guidelines [Scher, 2016].

Analysis of serum samples for testosterone is detailed below:

Testosterone Assessment

Serum concentrations of testosterone will be obtained as indicated in the Schedule of Activities (see Section 1.1).

Testosterone will be assayed using a liquid chromatography-tandem mass spectrometry method sensitive at least as low as 5 ng/dL (0.17 nmol/L) for all measurements.

Between Week 5 and Week 49 visits (inclusive), testosterone samples that are above castrate level (> 50 ng/dL) will be reported to the investigator at the respective study site. Testosterone samples may be subject to reanalysis by liquid chromatography/mass spectrometry and/or immunoassay sensitive to at least as low as 10 ng/dL.

Instructions for collection and processing of blood specimens are provided in the investigator site file.

